7.6.7.6 Progression-free survival

PFS is defined as the duration of time from date of assignment to treatment arm to time of objective progression or death, whichever occurs first (see Section 10.1).

7.6.8 Evaluation of best overall response

The best overall response is the best response recorded from the start of the treatment until disease progression/recurrence (taking as reference for progressive disease the smallest measurements recorded since the treatment started). The patient's best response assignment will depend on the achievement of both measurement and confirmation criteria.

TABLE 5 Best Overall Response For Patients with Measurable Disease (i.e. Target Disease)

Target Lesions	Non-Target Lesions	New Lesions	Overall Response	Best Overall Response when Confirmation is Required*
CR	CR	No	CR	≥4 wks. Confirmation
CR	Non-CR/Non-PD	No	PR	≥4 wks. Confirmation
CR	Not evaluated	No	PR	
PR	Non-CR/Non-PD/not evaluated	No	PR	
SD	Non-CR/Non-PD/not evaluated	No	SD	Documented at least once ≥4 wks. from baseline
PD	Any	Yes or No	PD	No prior SD, PR or CR
Any	PD**	Yes or No	PD	
Any	Any	Yes	PD	

* See RECIST 1.1 manuscript for further details on what is evidence of a new lesion.
** In exceptional circumstances, unequivocal progression in non-target lesions may be accepted as disease progression.

Note: Patients with a global deterioration of health status requiring discontinuation of treatment without objective evidence of disease progression at that time should be reported as “*symptomatic deterioration*.” Every effort should be made to document the objective progression even after discontinuation of treatment.

Table 6 Best Overall Response for Patients with Non -Measurable Disease (i.e., Non-Target Disease)

Non-Target Lesions	New Lesions	Overall Response
CR	No	CR
Non-CR/Non-PD	No	Non-CR/Non-PD*
Not all evaluated	No	Not evaluated
Unequivocal PD	Yes or No	PD
Any	Yes	PD

* ‘Non-CR/non-PD’ is preferred over ‘stable disease’ for non-target disease since SD is increasingly used as an endpoint for assessment of efficacy in some trials so to assign this category when no lesions can be measured is confusing.

7.6.9 Duration of combined radiographic and PSA response

Duration of combined radiographic and PSA response is measured from the time of first documented response (RECIST v1.1 CR/PR or PSA decline $\geq 50\%$) until death, recurrent or progressive disease (based on RECIST v1.1) or first PSA increase $\geq 25\%$ and ≥ 2 ng/ml above the PSA nadir.

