7.6 Efficacy

Response and progression will be evaluated in this study using a combination of the international criteria proposed by the RECIST Committee for measurable disease and the guidelines for prostate cancer endpoints developed by the Prostate Cancer Clinical Trials Working Group (PCWG3)[14] for bone metastasis.

Patients will need to be reevaluated for response according to the guidelines below.

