7.6.7 Progression/response criteria

Non-lethal disease progression (necessitating discontinuation from trial) is either clinical progression (see Section 7.6.7.5) or radiographic progression based on RECIST (see Section 7.6.7.1, 7.6.7.2) or PCWG3 bone scan criteria (see Section 7.6.7.4). These are combined and

shown in graphical format in Section 7.6.8. Confirmatory bone scan ≥ 4 weeks after first bone scan progression per PCWG3 is required and must show ≥ 2 new lesions.

PSA progression alone is NOT sufficient for removal from study.

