7.6.7.3 Outcomes based on radionuclide bone scans

The subjectivity in interpreting serial changes in a radionuclide bone scan is well recognized. Thus, the primary outcome will be whether the scan is stable or improved, vs. worse or progression. Changes in intensity will not be used as an outcome measure.

Stable or Improved: A stable or improved classification requires that no new lesions appear at the 3rd cycle (12 weeks) \pm 1 week assessments.

Progression (Non-Response): Appearance of **two or more** new skeletal lesions. *An increase in the size or intensity of known skeletal lesions will not be considered progression.* This must be confirmed with another bone scan \geq 4 weeks after first bone scan progression per PCWG3 and must show \geq 2 new lesions.

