7.6.7.4 Outcomes based on post-therapy PSA changes

These definitions are intended to characterize the PSA changes on study for the purpose of reporting of results. PSA progression is NOT criteria to remove from study.

Complete Response (CR): Undetectable PSA (\leq 0.2 ng/ml) that is confirmed by another PSA level at no less than 4 weeks interval.

Partial Response (PR): Decrease in PSA value by \geq 50% that is confirmed by another PSA level at no less than 4 weeks interval.

Stabilization (SD): Patients who do not meet the criteria for PR or PD for at least 90 days on study (2 cycles of treatment) will be considered stable

Progression (PD): 25% increase over baseline or nadir whichever is lower and an increase in the absolute value of PSA level by 2 ng/ml that is confirmed by another PSA level at no less than 4 weeks interval.

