10.1.2 Analysis of the secondary endpoints

- The response rate and 95% binomial confidence interval will be reported for DRDef patients.

The following endpoints will be reported for DRDef and DRPro patients separately

- Objective progression-free survival (combined radiographic and clinical progression-free survival) will be reported using Kaplan-Meier methods. This is measured from the date of treatment arm assignment until the specified tumor progression (assigned at the earliest observed time). Patients whose disease has not progressed at follow-up will be censored at the date when the last tumor assessment determined a lack of progression.
- Objective radiographic disease response rate is determined by the proportion of patients with measurable disease that have a response (CR+PR) according to RECIST v1.1. The proportion of responders will be reported with the corresponding 95% binomial confidence interval.
- PSA progression-free survival (PSA-PFS) will be reported as the composite of survival and duration of PSA control as defined by after a start of therapy from baseline to time of first PSA increase $\geq 25\%$ and ≥ 2 ng/mL above the nadir and confirmed by a second value at or beyond 4 weeks later. Kaplan-Meier methods will be used to report PSA-PFS.

- PSA response rate (≤ 0.2 ng/ml, 50% decline, 90% decline) proportions will be reported with corresponding 95% binomial confidence intervals. A waterfall plot of the best PSA response decline will be reported.
- Evaluate the qualitative and quantitative AE summaries will be reported by DNA repair status and organized by body system, frequency of occurrence, intensity (e.g. severity grade) and causality or attribution. Counts and proportions will be included. Treatment exposure will be summarized for all patients, including dose administration, number of cycles, dose modifications or delays and duration of therapy. Categorical variables will be reported using counts and frequencies. Continuous variables will be summarized using means or medians with the appropriate measure of variability.
- Duration of combined radiographic and PSA response will be reported using Kaplan-Meier methods.

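### Duration of response ends at a PSA rise with no stated confirmation and at RECIST progression only, out of step with the trial's own PSA, bone-scan and clinical progression rules

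*Combined protocol and SAP*

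**What the plan says.** **Duration of response.** Section 7.6.9 and the objectives tables in the synopsis and Section 2.2 share one definition. The clock starts at the first RECIST CR/PR or PSA decline of at least 50%. It runs "until death, recurrent or progressive disease (based on RECIST v1.1) or first PSA increase" of at least 25% and at least 2 ng/ml above nadir. Section 10.1.2 adds only that Kaplan-Meier methods will be used; it gives no censoring rule for this endpoint.

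**PSA progression.** Section 7.6.7.4 uses the same two thresholds but asks for a rise "in the absolute value of PSA level by 2 ng/ml that is confirmed by another PSA level" at least 4 weeks later. PSA progression-free survival (PSA-PFS) in Section 10.1.2 likewise needs a rise "above the nadir and confirmed by a second value at or beyond 4 weeks later". PSA partial response in 7.6.7.4 also needs confirmation.

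**Objective progression.** Section 7.6.7 says that non-lethal progression "is either clinical progression (see Section 7.6.7.5) or radiographic progression based on RECIST (see Section 7.6.7.1, 7.6.7.2) or PCWG3 bone scan criteria". Bone-scan progression means two or more new lesions, and Section 7.6.7.3 adds: "This must be confirmed with another bone scan" at least 4 weeks later. Section 7.6 uses RECIST for measurable disease and the guidelines of the "Prostate Cancer Clinical Trials Working Group (PCWG3)[14] for bone metastasis". Objective progression-free survival (PFS) in Section 2.2 counts radiographic progression, clinical decline and death.

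**Follow-up.** Section 5.6.2 follows patients for 30 days after removal from treatment, or until death if sooner.

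**The concern.** The same patient can have three progression histories. A responder with one transient PSA rise loses the response in 7.6.9, yet has no PSA progression under 7.6.7.4 and no PSA-PFS event. A responder taken off for pain progression has an objective PFS event, yet no duration-of-response event. Unless a PSA rise, RECIST progression or death falls within the next 30 days, he is censored while still counted as in response. That censoring is caused by progression, so it is informative, and Kaplan-Meier assumes that it is not.

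At stake is how the reported duration is interpreted in each cohort. Both faults can act at once and in opposite directions, so a reader could not correct the published figure.

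**Working it through.** **1. Figure to reproduce.** There is none. The documents give no expected median, event count or precision for duration of response, so the check compares definitions.

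**2. Event sets side by side.**

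| Event | Progression (7.6.7) | Objective PFS (2.2) | PSA-PFS (2.2, 10.1.2) | Duration of response (7.6.9) |
|---|---|---|---|---|
| Death | not applicable (non-lethal only) | yes | yes | yes |
| RECIST progression | yes | yes | no | yes |
| Bone scan, ≥2 new lesions, confirmed | yes | yes | no | not named |
| Clinical (pain) progression | yes | yes | no | no |
| PSA rise ≥25% and ≥2 ng/ml, confirmed | no | no | yes | yes |
| Same rise, not confirmed | no | no | no | yes, as worded |

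**3. Bone has two readings.** If Section 7.6 leaves bone to PCWG3, bone progression is outside 7.6.9. But Section 7.6.4 lists bone lesions as non-measurable disease, and Section 7.6.7.2 makes one or more new lesions progressive disease. On that RECIST reading a single unconfirmed bone lesion ends the response, against the confirmed two-lesion rule of 7.6.7 and 7.6.7.3. Two analysts could date the same patient differently.

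**4. Direction.** For each patient, let

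- D_aligned = min(death, RECIST, confirmed bone scan, clinical, confirmed PSA)
- D_plan = min(death, RECIST, any qualifying PSA rise)

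D_plan takes the PCWG3 reading of bone. Adding unconfirmed rises to a minimum can only move it earlier or leave it. Removing bone and clinical events can only move it later or leave it. The two changes oppose each other, so the definitions alone do not fix the net sign.

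**5. Illustration on assumed inputs.** None of these rates is in the documents.

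*False ends.* With PSA every 4 weeks (Section 7.6.1) and an assumed chance f per test of a rise that would not confirm, the chance of at least one false end in 6 tests is 1 − (1 − f)^6:

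- f = 1%: 1 − 0.99^6 = 5.9%
- f = 2%: 1 − 0.98^6 = 11.4%
- f = 5%: 1 − 0.95^6 = 26.5%
- f = 10%: 1 − 0.90^6 = 46.9%

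*Net effect.* This is a simulation of 200,000 responders with independent exponential times. Assumed medians are 8 cycles to PSA progression, 10 to RECIST progression, and 6, 10 or 20 to bone or clinical progression. PSA is read every cycle and scans every second cycle. Follow-up is complete. Mean duration in 4-week cycles:

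| Bone/clinical median | Aligned | Plan, f = 0 | Plan, f = 2% | Plan, f = 5% | Plan, f = 10% |
|---|---|---|---|---|---|
| 6 | 4.56 | 7.14 | 6.38 | 5.51 | 4.49 |
| 10 | 5.28 | 7.13 | 6.37 | 5.50 | 4.48 |
| 20 | 6.05 | 7.16 | 6.40 | 5.53 | 4.49 |

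In the middle row, the missing confirmation alone lowers 5.28 to 4.89, 4.40 or 3.77 (f = 2%, 5%, 10%), and omitting bone and clinical events alone raises it to 7.13. Combined, the plan's definition lengthens duration at 2% and 5% and shortens it at 10%. With a bone/clinical median of 20, it already shortens it at 5%.

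*Censoring.* If patients instead leave at bone or clinical progression and are followed one further cycle, 7% to 33% of responders across these scenarios are censored for a reason tied to progression.

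**The case against.** **The missing confirmation may be shorthand.** Section 7.6.7.4 says that its definitions serve the reporting of results, and the PSA-PFS definition also speaks of a first increase while requiring confirmation. So the word first does not by itself waive confirmation. This stands as a possible reading. But in the objectives tables the PSA-PFS row states confirmation and the duration row does not, so the literal reading is that the two differ.

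**Bone progression is not simply ignored.** A reader might infer that bone progression never ends a response. The documents do not support that, because RECIST's new-lesion rule could capture it. That route brings a different conflict, and pain progression is outside 7.6.9 on either reading.

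**Composites may differ.** A reader might treat any response that ends before PSA-PFS as an error. It is partly expected: duration of response counts RECIST progression and PSA-PFS does not. Nor does ending a combined response on PSA contradict the rule that a PSA rise alone is not progression, which governs study progression and removal. The PSA fault is only the missing confirmation.

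**Pain is a debatable event.** Section 7.6.7.5 can be met by one parenteral opioid dose for cancer pain. Whether that should end a tumor or PSA response is a design choice, but the plan should make it openly and say how such patients are censored.

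**Precision is poor anyway.** At the 20% target, 35 DRPro patients give 0.20 × 35 = 7 responders. With 7 exponential events, the 95% interval for the median runs from 14/26.12 = 0.54 to 14/5.63 = 2.49 times the estimate (chi-square, 14 df). This limits the practical weight of the point, but sampling error does not excuse an inconsistent event definition.

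**Conclusion.** The point holds as an inconsistency in a secondary, descriptive endpoint that should be corrected. The definition omits the confirmation that the trial requires elsewhere at identical PSA thresholds. It leaves out clinical progression, and it treats bone progression in one of two ways, neither matching 7.6.7.

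The direction of each component follows from the definitions. The size and net sign do not: they depend on how often PSA rises fail to confirm and on how many responders progress first in bone or clinically, and the documents give neither. A reader might infer a definite net shortening from the PSA rule alone, or a definite lengthening from the omitted events. Neither is supported, and the illustration changes sign within its assumed range.

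The primary response rate and both Simon decision rules count responses and do not use the end date, so they are unaffected.

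**What to change.** In the synopsis, Section 2.2 and Section 7.6.9:

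- **End** duration of response at the earliest of death; objective progression as already defined in 7.6.7 (RECIST, confirmed PCWG3 bone scan, or clinical); or PSA progression confirmed per 7.6.7.4 and dated at the first rise.
- **Start** a PSA-based response only if it is confirmed per 7.6.7.4, dated at the first qualifying decline. Otherwise only one end of the interval is aligned.
- **Censor** patients without an event at the last adequate assessment, and state in Section 10.1.2 how a final PSA rise or bone scan that could not be confirmed is handled.

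While editing, correct the cross-reference in 7.6.7, which sends the reader to 7.6.7.4 for bone-scan criteria that sit in 7.6.7.3.

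The cost is mainly wording. PSA is measured about every 4 weeks on treatment, Section 5.6 does not stop therapy for a PSA rise alone, bone-scan confirmation is already required, and clinical progression is already needed for objective PFS. There is a small downside. Follow-up after treatment is 30 days, the end-of-treatment visit has a window of ±3 days, and the study calendar appears to schedule no imaging then. Some last rises or scans will lack a confirmatory value, which is why the handling rule is needed.

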7.7 Safety

The Principal Investigator is responsible for ensuring that all staff involved in the study is familiar with the content of this section.

7.7.1 Adverse event reporting requirements

Adverse event (AE) monitoring and reporting is a routine part of every clinical trial and is done to ensure the safety of subjects enrolled in the studies as well as those who will enroll in future studies using similar agents. Data on adverse events will be collected from the time of the initial study treatment administration through 30 days after the last dose of study treatment. Any serious adverse event that occurs more than 30 days after the last study treatment and is considered related to the study treatment will be reported to sponsor investigator. Serious Adverse Events (SAEs) will continue to be followed until:

- Resolution or the symptoms or signs that constitute the serious adverse event return to baseline;
- There is satisfactory explanation other than the study treatment for the changes observed; or
- Death.

The investigator is responsible for the detection, documentation, grading and assignment of attribution of events meeting the criteria and definition of an AE or SAE. The definitions of AEs and SAEs are given below. It is the responsibility of the principal investigator to ensure that all staff involved in the trial is familiar with the content of this section.

Any medical condition or laboratory abnormality with an onset date before initial study treatment is considered to be pre-existing in nature. Any known pre-existing conditions that are ongoing at time of study entry should be considered medical history.

All events meeting the criteria and definition of an AE or SAE, as defined in this section, occurring from the initial study treatment through 30 days following the last dose of the study treatment must be recorded as an adverse event in the patient's source documents and on the CRF regardless of frequency, severity (grade) or assessed relationship to the study treatment. In addition to new events, any increase in the frequency or severity (i.e., toxicity grade) of a pre-existing condition that occurs after the patient begins study treatment is also considered an adverse event.

Adverse events after the 30 day follow up period

For Pharmacovigilance purposes and characterization, any SAE of MDS/AML or new primary malignancy occurring after the 30 day follow up period should be reported to AstraZeneca Patient Safety regardless of investigator's assessment of causality or knowledge of the treatment arm. After study completion, vigilance will be maintained by either a) annual

chart review for the diagnosis or b) phone call asking the patient whether they have been diagnosed with MDS/AML or a new malignancy (one of these should happen between months 10-12 after discontinuation). If a patient has been diagnosed with MDS/AML or another malignancy, a questionnaire may be sent to them for further information. This will continue for 5 years after a patient completes study.

At any time after a patient has completed the study, if an Investigator learns of any SAE including sudden death of unknown cause, and he/she considers there is a reasonable possibility that the event is causally related to the investigational product, the investigator should notify the Principal Investigator who will notify AstraZeneca, Patient Safety.

7.7.2 Definition of adverse events

An adverse event (AE) is any untoward medical occurrence in a patient receiving study treatment and which does not necessarily have a causal relationship with this treatment. An AE can be any unfavorable and unintended sign (including an abnormal laboratory finding), symptom, or disease temporally associated with the use of an experimental intervention, whether or not related to the intervention.

- Diagnostic and therapeutic non-invasive and invasive (i.e., surgical) procedures will not be reported as adverse events. However, the medical condition for which the procedure was performed must be reported if it meets the definition of an adverse event unless it is a pre-existing (prior to protocol treatment) condition.
- Symptoms of prostate cancer are not to be considered adverse events for this study. The following symptoms are indicative of underlying disease and will not be reported as adverse events (unless the event is considered serious): bone pain, urinary frequency, hesitancy or urgency.
- Abnormal laboratory values or test results constitute adverse events if they induce clinical signs or symptoms or require therapy. They are to be captured under the signs, symptoms or diagnoses associated with them.

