 - a. Hemoglobin ≥ 10 g/dL (with no blood transfusion or erythropoietin use within the past 42 days)
 - b. Absolute neutrophil count $\geq 1.5 \times 10^9$ /L
 - c. Platelet count $\geq 100 \times 10^9$ /L (with no platelet transfusions within last 42 days)
 - d. Total bilirubin $< 1.5 \times$ ULN (unless the patient has documented Gilbert's disease and $< 2.0 \times$ ULN should be used)
 - e. AST or ALT $\leq 2.5 \times$ ULN, unless liver metastases are present in which case they cannot be $\geq 5 \times$ ULN
 - f. Glomerular filtration rate (GFR) ≥ 51 mL/min, as assessed using the Cockcroft-Gault equation
13. Estimated life expectancy ≥ 16 weeks
14. Male patients who are sexually active must be willing to use barrier contraception for the duration of the study and for 1 week after the last study drug administration, with all sexual partners. Male patients must use a condom during treatment and for 6 months after the last dose of study drug(s) when having sexual intercourse with a pregnant woman or with a woman of childbearing potential and must not donate sperm for 6 months after the last dose of study drug. Female partners of male patients should also use a highly effective form of contraception (see Appendix C) for 6 months after the last dose of study drug(s) if they are of childbearing potential. True abstinence is an acceptable form of contraception and must be documented as such.
15. Patient is willing and able to comply with the protocol for the duration of the study, including undergoing biopsy (if warranted), treatment, scheduled visits and examinations

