5.4.3 Hematologic Day 1 dosing requirement

Hematologic toxicity is anticipated to be the biggest challenge. To minimize this risk, there are clear Day 1 criteria (for any cycle) for both ANC and platelets. Both an ANC over 1000/ μ L and platelets over 75,000/ μ L are required to start each cycle. If either parameter is not met, treatment is delayed. If the patient has not recovered after 28 days, they are removed from protocol and please see section 5.13 for further hematologic workup.

TABLE 3 Day 1 minimum hematologic criteria

Treatment day blood counts and toxicity			
ANC		Platelets	Action
$\geq 1000/\mu\text{L}$	AND	$\geq 75,000/\mu\text{L}$	No dose modification or interruption
$< 1000/\mu\text{L}$	OR	$< 75,000/\mu\text{L}$	Delay by 1 week intervals until recovery

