5.4.4 Management of anemia

Olaparib has shown the most suppression of red blood cells in prior studies, such that it is first reduced in lower risk anemia scenarios. At development of anemia, appropriate supportive treatment should be considered (per local guidelines) and alternate cause evaluation considered (e.g. iron, vitamin B12, folate, hypothyroidism). Investigator judgement to continue study treatment with or without supportive treatment (e.g. transfusion) or interrupt dose for a maximum of 4 weeks per guidance below. The use of erythropoietin is not allowed. For cases where patients develop prolonged hematologic toxicity causing >2-week interruption/delay in study treatment for CTCAE Grade 3 or worse anemia and/or blood transfusion dependence, refer to Section 5.4.14 for workup to consider.

Note, if at any time a dose reduction for a drug is required and the patient is already at dose level -2 for that drug, the patient must be removed from study.

Symptoms related to the Anemia (e.g. fatigue, shortness of breath) are designated by treating provider.

ASYMPTOMATIC Grade 2 Anemia (Hgb<10 and Hgb≥8 g/dL):

Asymptomatic Grade 2 anemia may be monitored and treatment continued without required delay or dose reduction. Delay, dose reduction and transfusions may be done at provider's discretion.

SYMPTOMATIC Grade 2 Anemia (Hgb<10 and Hgb≥8 g/dL) or ANY Grade 3 Anemia (Hgb<8 g/dL):

First episode:

1. Symptomatic Grade 2:

A treatment delay up to 28 days maximum (with or without blood transfusion) to allow resolution to asymptomatic Grade 2, Grade 1 or lower. Olaparib may be dose reduced or continued at current dose level.

2. Grade 3:

Treatment is delayed to allow resolution to asymptomatic Grade 2, Grade 1 or lower (up to 28 days maximum). Transfusions may be done at provider's discretion. Upon recovery, olaparib is reduced by one dose level (if possible).

Second episode:

3. Symptomatic Grade 2:

A treatment delay up to 28 days maximum (with or without transfusion) to allow resolution to asymptomatic Grade 2, Grade 1 or lower. Upon recovery, Olaparib is dose reduced by one level (if possible).

1. If olaparib was at full dose, AZD6738 dose/schedule is unchanged.
2. If olaparib was at dose level -1, AZD6738 is moved down one dose level. Either from dose level 0 to dose level -1 (hematologic toxicity, which is 160 mg daily Days 1-4) OR from dose level -1 (hematologic or non-hematologic) to dose level -2.

4. Grade 3:

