10.3 Safety Analysis

10.3.1 Evaluation of adverse events

Treatment-emergent AEs will be translated from investigator terms to a custom medical dictionary and summarized (number and percentage of patients) for each treatment arm for all patients who receive at least one dose. AE summaries will be reported by arm and organized by body system, frequency of occurrence, intensity (i.e., severity grade), and causality or attribution. Patients who experience an AE more than once will be counted only once. The occurrence with the maximum severity will be used to calculate intensity.

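### The Section 7.7.2 laboratory bullet could keep asymptomatic, untreated cytopenias out of the adverse event tables, and Section 10 plans no laboratory-grade table that would show them

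*Combined protocol and SAP*

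**What the plan says.** **AE definition (7.7.2).** The opening sentences are broad and allow an abnormal laboratory finding to be an AE in itself. Three bullets follow. The first two remove procedures and certain disease symptoms. The third reads: "Abnormal laboratory values or test results constitute adverse events if they induce clinical signs or symptoms or require therapy". Such values are then filed under the associated sign, symptom or diagnosis.

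**Recording duty (7.7.1).** Events must be recorded whatever their grade, but only if they meet the section's definition. On baseline abnormalities: "Any medical condition or laboratory abnormality with an onset date before initial study treatment is considered to be pre-existing in nature". It also counts as an AE "any increase in the frequency or severity (i.e., toxicity grade) of a pre-existing condition" arising after treatment starts, and this rule has no symptom or therapy condition.

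**Expected toxicity.** Section 5.4.3 says: "Hematologic toxicity is anticipated to be the biggest challenge". It sets Day 1 minimum ANC and platelet counts, and: "If either parameter is not met, treatment is delayed". Section 5.4.4 says: "Asymptomatic Grade 2 anemia may be monitored and treatment continued without required delay or dose reduction".

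**Planned safety output.** Section 2.3 answers the safety objective with AE summaries and exposure by genetic subtype. Sections 10.1.2 and 10.3.1 to 10.3.3 plan AE tables built from investigator terms, separate summaries of SAEs and of AEs leading to withdrawal or death, and an exposure summary. In the AE tables: "Patients who experience an AE more than once will be counted only once", at maximum severity.

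**The concern.** Cytopenias are found on a blood count and are often silent. If a site takes the 7.7.2 bullet as its test for laboratory AEs, a low count that causes no symptoms and receives no treatment is not entered as an AE. No other planned table would show it. The reader of the safety results would then see cytopenia rates that depend partly on how each site read one sentence. The exposure table could also show a delayed cycle with no matching AE. This matters because tolerability by cohort is a stated objective and the cohorts are small.

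**Working it through.** **1. Which reading of the bullet is natural?** The opening of 7.7.2 already admits abnormal laboratory findings, and the two preceding bullets both narrow that opening. Unless the third bullet narrows it too, it adds little. Against this, it says *if*, not *only if*. The 7.7.1 worsening rule has no symptom condition. Sections 5.4.3 to 5.4.5 handle cytopenias by grade or count, including asymptomatic ones, and 5.4.5 calls neutropenia and leukopenia adverse events. The documents do not say which text prevails.

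**2. Does the baseline value matter?** Entry requires "Hemoglobin ≥ 10 g/dL" (4.1), and 5.4.4 defines grade 2 anemia as 8 to below 10 g/dL. Take two patients who fall to 9.0 g/dL without symptoms or therapy, and assume a laboratory lower limit above 10 g/dL.

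| Reading | Baseline 10.5 (below the laboratory limit) | Baseline normal |
|---|---|---|
| Broad reading throughout | AE | AE |
| Bullet governs all laboratory values | Not an AE | Not an AE |
| Bullet for new values, 7.7.1 for worsening | AE | Not an AE |

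Only the third row treats the same value differently. The second and third rows can both lose cases.

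**3. Can serious grades be lost?** An ANC below 1000/µL delays a cycle (5.4.3), and 5.4.14 classes it as grade 3 or worse. Primary G-CSF is not allowed (4.3.2), so delay alone may be the management. Nothing says whether a delay counts as therapy under the bullet.

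**4. Does other text fill the gap?**
- Ongoing review of laboratory data by the lead site (9.6) is not a tabulation.
- Summary statistics (10.3.5) and change from baseline (10.3.7) do not name laboratory values or grades.
- Source verification and queries (7.1, 7.5) can find missing entries but do not settle which rule a monitor should apply.
- Reasons for dose changes are recorded (5.4.2), but 10.3.3 states no breakdown by reason. A cytopenia with no dose change leaves no dose record.

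**5. Scale.** If *k* patients have a cytopenia omitted and no other recorded episode of that AE, incidence falls by *k*/*n*. The documents give no *k*, and it may be 0. For *k* = 1:
- DRPro: 1/35 = 2.9 points
- DRDef: 1/12 = 8.3 points
- Overall: 1/47 = 2.1 points
- If DRPro stops after stage 1: 1/17 = 5.9 points in DRPro and 1/(17 + 12) = 1/29 = 3.4 points overall

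The safety set is all treated patients (10.2.2), so actual denominators may differ. If another episode is recorded, incidence is unchanged, but the reported maximum grade could still be too low.

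**6. What can scheduled CBCs show?** Per the study calendar, the C2D8 CBC is optional and from cycle 3 only Day 1 is scheduled, with a window of −5 to +3 days. Day 1 of the next cycle is Day 29 of the current one. Assuming no dose delay, the time from the last AZD6738 dose to the next scheduled CBC is:
- Day 1–7 schedule: 29 − 7 = 22 days (17 to 25 with the window)
- Day 1–4 schedule (reduced levels in Table 1): 29 − 4 = 25 days (20 to 28)

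A mid-cycle low can therefore be missed, so a table from these counts gives a lower bound.

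**The case against.** The strongest reply is that the bullet does not exclude anything. It says *if*, the opening definition covers laboratory findings, and the toxicity sections treat silent cytopenias as graded toxicities. A site could record every one of them. This stands, and it is why the point is a possible gap rather than a demonstrated one.

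A reader might infer a firm contradiction, with the same hemoglobin value being an AE or not according to baseline. The documents do not support that. It needs the restrictive reading for new abnormalities and the broad rule for worsening ones. The 7.7.1 worsening sentence speaks of a condition, so the laboratory bullet can equally be taken to govern at every baseline. That would be one consistent rule, though still one that omits silent cases.

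It is also fair that the one-patient figures are reciprocals of sample size and show no actual effect, that scheduled CBCs are data a monitor can check, and that a cycle delay has a recorded reason. For anemia the interval since AZD6738 says little, because 5.4.4 attributes most red-cell suppression to olaparib, given on all 28 days. None of this supplies a planned output in which an unrecorded cytopenia would appear.

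**Conclusion.** The point holds as an ambiguity in what is recorded, combined with a missing table. On the natural reading of the 7.7.2 bullet, asymptomatic and untreated cytopenias could be absent from the only planned toxicity tables, including an ANC below 1000/µL managed by delay alone. The size cannot be derived from the documents and may be zero.

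A reader might go further and infer that the reported rates are understated, or that the two cohorts are distorted differently. Neither follows. The same recording text applies to both cohorts, and nothing in the documents shows how sites read it.

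The primary endpoint, SAEs, symptomatic or treated cytopenias and the 25% toxicity stopping rule, which counts removals from treatment, are unaffected. The change is worth making because the safety objective rests on these tables and the remedy is cheap.

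**What to change.** - **Section 10.3.1:** add a table, by cohort and overall for all treated patients, of worst post-baseline CTCAE v5.0 grade, with baseline grade, for hemoglobin, WBC, ANC and platelets. Use the scheduled CBCs plus any unscheduled ones in the database. Place it beside the AE table, which keeps attribution. Label it a lower bound and give the sampling reasons in step 6.
- **Section 10.3.3:** tabulate delays, reductions and discontinuations by the reason recorded in the eCRF.
- **Separately:** reconcile 7.7.1 and 7.7.2 so that one stated recording rule applies whatever the baseline value. The tables do not depend on this. If the rule changes mid-study, report that AE ascertainment differs before and after.

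**Cost:** one or two extra tables and no new tests. Rewording may add some AE entry and brings the before/after difference. The tables avoid both and are worth adding even if enrollment is complete.
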